	clinical study report (sections 16.1 and 16.2 according to ICH E3)	. 29

Sponsor: Laboratorios Salvat, S.A. Study Code: CLOBOF3-16IA01

NCT No.: NCT04246801

ABBREVIATIONS

ΑE Adverse Event

AESI Adverse Event of Special Interest ATC **Anatomical Therapeutic Chemical**

BCVA Best-Corrected Visual Acuity

BMI **Body Mass Index**

CSR Clinical Study Protocol

eCRF Electronic Case Report Form

FAS Full Analysis Set

ICH International Conference on Harmonization

IMP **Investigational Medicinal Product**

IOP Intraocular Pressure

Medical Dictionary for Regulatory Activities MedDRA

MMRM Mixed Model of Repeated Measures **NSAID** Non-Steroidal Anti-Inflammatory Drug

PP Per Protocol PT Preferred Term Q1 25th percentile Q3 75th percentile

QID Four times a day (Quater In Die) REML Restricted Maximum Likelihood

SAE Serious Adverse Event SAF Safety Analysis Set

SAP Statistical Analysis Plan

SOC System Organ Class

STEAE Serious Treatment-Emergent Adverse Event

SUN Standardization of Uveitis Nomenclature

TEAE Treatment-Emergent Adverse Event

VAS Visual Analog Scale

WHO World Health Organization

Date: 09-JUL-2021

Sponsor: Laboratorios Salvat, S.A. Study Code: CLOBOF3-16IA01 NCT No.: NCT04246801

1 INTRODUCTION

This Statistical Analysis Plan (SAP) is based on Clinical Study Protocol (CSP) Version 2.0 FINAL Amendment 1 dated February 26, 2020.

2 STUDY OBJECTIVES

2.1 Primary Objective

To assess the effect of clobetasol propionate ophthalmic nanoemulsion 0.05% on ocular inflammation associated with cataract surgery after one week of treatment.

2.2 Secondary Objectives

Key secondary objective

Efficacy:

• To assess the effect of clobetasol propionate ophthalmic nanoemulsion 0.05% on eye pain associated with cataract surgery after one week of treatment.

Other secondary objectives

Efficacy:

- To assess the effect of clobetasol propionate ophthalmic nanoemulsion 0.05% on ocular inflammation associated with cataract surgery
- To assess the effect of clobetasol propionate ophthalmic nanoemulsion 0.05% on eye pain and on eye discomfort associated with cataract surgery

Safety:

 To evaluate the safety and tolerability of clobetasol propionate ophthalmic nanoemulsion 0.05%

Sponsor: Laboratorios Salvat, S.A. Study Code: CLOBOF3-16IA01 NCT No.: NCT04246801

3 **ENDPOINTS**

3.1 **Primary Efficacy Endpoint**

Proportion of patients with anterior chamber cell grade of "0" (absence of cells) compared to placebo at Day 8.

Anterior chamber cell grade will be assessed by the investigator during slit-lamp examination and will be graded on an adapted 6-point scale proposed by the Standardization of Uveitis Nomenclature (SUN) working group (Table 1).

Calla in field*

Table 1. Grading scheme for anterior chamber cells

^{*}Field size is a 1mm by 1 mm slit beam

[figure not shown]
Grade	Cells in field*			
0	0			
0.5+	1-5			
1+	6-15			
2+	16-25			
3+	26-50			
4+	>50			
*Field size in a dame but dame alik beare				

3.2 **Secondary Efficacy Endpoints**

Key secondary efficacy endpoint

Proportion of patients with VAS pain score of "0" (no eye pain) compared to placebo at Day 8.

Eye pain score will be assessed by the patient before any ocular examination and will be scored by ticking on a continuous scale comprised of a 10 cm horizontal line anchored by two verbal descriptions: "no eye pain" (score of 0) and "worst imaginable eye pain" (score of 10).

The records to be considered are those whose date coincides with the visit to be analyzed for VAS pain score except in model to analyze the change over time in the VAS pain score reported every day compared to placebo.

Proportion of patients with anterior chamber cell grade of "0" compared to placebo at Day 3, Day 15 and Day 29.

Version: Final 3 Study Code: CLOBOF3-16IA01
Date: 09-JUL-2021 NCT No.: NCT04246801

• Change from Baseline to Day 3, Day 8, Day 15 and Day 29 compared to placebo in the proportion of patients with different anterior chamber cell grades.

Sponsor: Laboratorios Salvat, S.A.

- Change from Baseline to Day 3, Day 8, Day 15 and Day 29 compared to placebo in the proportion of patients with different anterior chamber flare grades.
- Proportion of patients with anterior chamber cell grade of "≤0.5+" and flare grade of "0" compared to placebo at Day 3, Day 8, Day 15 and Day 29.
- Proportion of patients with anterior chamber cell grade of "≤1+" compared to placebo at Day 3, Day 8, Day 15 and Day 29.
- Proportion of patients with anterior chamber cell grade of "0" and flare grade of "0" compared to placebo at Day 3, Day 8, Day 15 and Day 29.
- Frequency of different signs of ocular inflammation compared to placebo at Baseline, Day 3, Day 8, Day 15 and Day 29.
- Change from Baseline to Day 3, Day 8, Day 15 and Day 29 compared to placebo in the proportion of patients with different signs of ocular inflammation.
- Change from Baseline to Day 3, Day 8, Day 15 and Day 29 compared to placebo in the severity of signs of ocular inflammation.
- Change from Baseline to Day 3, Day 8, Day 15 and Day 29 compared to placebo in the visual analog scale (VAS) photophobia score.
- Change from Baseline to Day 8, Day 15 and Day 29 compared to placebo in Snellen bestcorrected visual acuity (BCVA) score.
- Change from Baseline to Day 3, Day 8, Day 15 and Day 29 compared to placebo in the VAS pain score.
- Proportion of patients with VAS pain of "0" compared to placebo at Day 3, Day 15 and Day 29.
- Change from baseline to Day 3, Day 8, Day 15 and Day 29 compared to placebo in the proportion of patients with different discomfort grades.
- Proportion of patients with no discomfort ("None") compared to placebo at Day 3, Day 8, Day 15 and Day 29.
- Change over time in the VAS pain score reported in the patients' diaries compared to placebo.

See previous section 3.1 for anterior chamber cell grade and key secondary efficacy endpoint of this section for eye pain VAS score.

- Anterior chamber cell flare will be assessed by the investigator during slit-lamp examination and will be graded on a 5-point scale proposed by SUN working group.

Table 2. The SUN working group grading scheme for anterior chamber flare

Grade	Description
0	None
1+	Faint
2+	Moderate (iris and lens details clear)
3+	Marked (iris and lens details hazy)
4+	Intense (fibrin or plastic aqueous)

Statistical Analysis Plan Sponsor: Laboratorios Salvat, S.A. Version: Final 3 Date: 09-JUL-2021

Study Code: CLOBOF3-16IA01 NCT No.: NCT04246801

Signs of ocular inflammation (chemosis, bulbar conjunctival injection, ciliary injection, corneal edema, keratic precipitates) will be assessed by the investigator during slit-lamp examination. Additionally, the severity of these signs of ocular inflammation will be assessed.

Table 3. Signs of ocular inflammation. Chemosis, bulbar conjunctival injection, ciliary injection, corneal edema and keratic precipitates.

Grade	Description
0	None
1	Mild
2	Moderate
3	Severe

Other: The severity of any other sign of ocular inflammation encountered by the investigators (e.g. hypopion, anterior chamber fibrinoid reaction, miosis, papilar or follicular conjunctival reaction, corneal neovascularization) will not be analyzed. They will only be shown in the listings.

- Monocular visual acuity will be completed with the patient's best correction vision in place using the standardized visual acuity measurement **Snellen** Test.
- The eye discomfort will be assessed by using the following categorical scale (Table

Table 4. Eye discomfort

Grade	Description
0	None
1	Mild
2	Moderate
3	Severe

The records to be considered are those whose date coincides with the visit to be analyzed for eye discomfort.

The photophobia VAS is a single-item continuous scale comprised of a 10 cm horizontal line anchored by two verbal descriptors, one for each symptom extreme. For photophobia intensity, the scale is anchored by "no photophobia" (score of 0) and "worst imaginable photophobia" (score of 10 cm). The photophobia VAS is completed by the patient:

Sponsor: Laboratorios Salvat, S.A. Study Code: CLOBOF3-16IA01 NCT No.: NCT04246801

The records to be considered are those whose date coincides with the visit to be analyzed for photophobia VAS.

3.3 Secondary Safety Endpoints

- Number, frequency and severity of adverse events (AEs) up to Day 29.
- Number, frequency and severity of serious AEs (SAEs) up to Day 29.
- Proportion of patients discontinuing the study due to AEs.
- Proportion of patients discontinuing the study due to lack of efficacy.
- Change from Baseline to Day 3, Day 8, Day 15 and Day 29 compared to placebo in intraocular pressure (IOP).
- Change from Baseline to Day 3, Day 8, Day 15 and Day 29 compared to placebo in physical and eye examination parameters and vital signs.
- Use of concomitant medications up to Day 29

The IOP will be assessed in both eyes using the Goldmann applanation tonometry method (for details see Appendix 3 of CSP).

4 OVERALL STUDY DESIGN

[figure not shown]
4.1 Overview of Study Design

This is a Phase 3, randomised, parallel-group, placebo-controlled, double-masked, multicentre study to assess the efficacy and safety of clobetasol propionate ophthalmic nanoemulsion 0.05% in the treatment of inflammation and pain associated with cataract surgery.

All randomized patients will undergo routine cataract surgery according to the investigator's normal procedures being surgery day considered Day -1 of the study, whereas the day of the randomization/first administration will be considered study Day 1. First administration of the Investigational Medicinal Product (IMP) will take place at the study center, whereas the rest of study medication will be dispensed to patients for self-administration at a dosage of one drop every six hours, four times a day (QID) during 14 days as well as a diary to record the drug instillations.

Sponsor: Laboratorios Salvat, S.A. Study Code: CLOBOF3-16IA01 NCT No.: NCT04246801

Figure 1. Diagram of Study Design

* Patients who, for any reason, withdraw from the study treatment will be highly encouraged to continue attending all their remaining study visits to collect the most complete efficacy and safety data.

4.2 Determination of Sample Size

At least 210 patients from approximately 20 sites in the U.S. will participate in this study. Patients will be randomized in a 2:1 ratio to receive either clobetasol propionate ophthalmic nanoemulsion 0.05 % (N=140) or placebo (N=70) for the treatment of inflammation and pain associated with cataract surgery. Dropouts will not be replaced since the expected dropout rate is low (4%).

The sample size calculation is based on a two group $\chi 2$ test with a 0.05 two-sided significance level will have 80% power to detect the difference between a proportion with complete resolution of anterior chamber cells in the active group of 0.22 and the placebo group proportion of 0.07 (odds ratio of 3.747) when the sample size is 202.

5 DATA SETS TO BE ANALYSED

The following analysis sets will be used for the statistical analysis and presentation of data:

• Full Analysis Set (FAS): The FAS will be the primary analysis set for the efficacy endpoints and will include all randomized patients. The FAS population will be analyzed according to the planned treatment (rather than treatment actually received).

Statistical Analysis Plan Sponsor: Laboratorios Salvat. S.A. Version: Final 3 Study Code: CLOBOF3-16IA01 Date: 09-JUL-2021

NCT No.: NCT04246801

Full Analysis Set without including rescued subjects (FAS non-RM set): The FAS non-RM will be the analysis set for the efficacy endpoints and will include all randomized patients without including rescued subjects (prohibited medication allowed.

- Safety Analysis (SAF) set The safety set will be the primary analysis set for the safety endpoints and will include all randomized patients who instilled at least one dose of IMP or placebo. The SAF will be analyzed according to the treatment actually received.
- Per Protocol (PP) Population: The PP population set will be tested to confirm the robustness of the efficacy analyses and will include all patients in the FAS who have no major protocol deviations (i.e. patients who comply the protocol sufficiently to ensure that the data exhibits the effects of the IMP or placebo when administered as intended). Protocol violations include: violations of entry criteria, lack of compliance and the use of prohibited medication. The PP population will be analyzed according to the treatment actually received.

Lack of compliance is defined as less than 80% compliance (section 6.3.8).

Efficacy analyses will be based on both the FAS and the PP, but the FAS will be considered the primary analysis population.

Safety analyses will be based on the SAF.

Primary efficacy and key secondary efficacy analysis will be performed for all efficacy endpoints, analyzing:

-all subjects who were randomized (i.e., FAS set),

AND

-all subjects who were randomized without including rescued subjects (i.e., FAS non-RM set)

Secondary efficacy analysis will be performed analyzing all subjects included in the FAS non-RM populations, hereinbefore described.

Sensitivity analysis described in the section 6.3.7 will be performed analyzing all subjects included in FAS set populations, hereinbefore described.

For the efficacy endpoints based in PP population (primary efficacy analysis and key secondary at visit 3) will include all patients in the FAS population who have no major protocol deviations. Without violations of eligibility criteria, lack of compliance at visit 3 (see section 6.3.8 for details) and without the use of rescue/prohibited medication until visit 3.

Only study eye will be analysed and presented in tables and the non-study eye will only be included in listings.

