Summary statistics

In general, data will be summarized by means of summary statistics. Continuous data will be presented with the number of observations, mean value, confidence intervals, standard deviation, minimum, Q1, median, Q3 and maximum value. Change from baseline to each post-baseline visit will be also described using descriptive statistics. Categorical data will be presented as counts and percentages.

The data will be presented for each treatment group by visit.

Individual patient data will be listed for all enrolled patients. Listings will be sorted by center and patient number and labelled by randomized treatment group.

Missing data

Data not collected after rescue therapy has been initiated will not be considered missing since the primary measure is a responder measure where rescue is considered treatment failure. Patients with missing data for the analysis of the primary endpoint will be assigned the status of treatment failure.

Primary analysis

The aim of the primary analysis of this study is to assess the superiority of clobetasol propionate ophthalmic nanoemulsion 0.05% compared to placebo with respect to the primary endpoint in the FAS.

The primary analysis will be based on a single study eye for each patient. Each patient's study eye will be defined as the surgery eye.

The test will be the proportion of study eyes with complete clearing of anterior chamber cells (count cell = 0) at Visit 3 (Day 8 ± 1 day) without receiving rescue medication as compared between clobetasol propionate ophthalmic nanoemulsion 0.05% dosed QID and placebo dosed QID using the chi square statistic.

The PP population set will be also tested to confirm the robustness of the primary analysis.

Key Secondary Analysis

The aim of the key secondary analysis of this study is to assess the superiority of clobetasol propionate ophthalmic nanoemulsion 0.05% compared to placebo with respect to the key secondary endpoint in the FAS.

The key secondary analysis will be based on a single study eye for each patient. Each patient's study eye will be defined as the surgery eye.

The test will be the proportion of study eyes with no pain (VAS pain = 0) at Visit 3 (Day 8 ± 1 day) without receiving rescue medication as compared between clobetasol propionate ophthalmic nanoemulsion 0.05% dosed QID and placebo dosed QID using the chi square statistic.

The PP population set will be also tested to confirm the robustness of the key secondary analysis.

Secondary analysis

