6.7.2 Rescue Medication

Any patients not responding adequately to the IMP may be rescued and placed on alternate therapy (Section 6.7) at the investigator's discretion at any time.

The choice of rescue medication is at the investigator's discretion. Any patient placed on rescue therapy will discontinue the use of the IMP and the investigator must made extensive efforts to ensure that the patient will attend all his/her remaining study visits until study completion, aiming to collect the most complete efficacy and safety data.

Additionally, patients will be asked to phone the study center at any time to speak to a member of the medical personnel should they experience any worsening of ocular conditions or other AFs

Rescued patients will be considered treatment failures, but the need for rescue therapy will not be considered an AE.

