6 STATISTICAL AND ANALYTICAL PLANS

The planned tables and listings are presented in Section 8.

Changes in the Planned Analyses 6.1

The SAP presented in this document will supersede the statistical analysis methods described in the clinical protocol. Any deviations/changes from the planned analyses described in this

Sponsor: Laboratorios Salvat, S.A. Study Code: CLOBOF3-16IA01 NCT No.: NCT04246801

document will be identified, with justification, in the appropriate section of the clinical study report (CSR).

Any changes in the statistical analyses once the SAP has been finalised and the database has been locked should be documented at clinical study report (CSR).

VAS is one of the most commonly used measures for pain intensity in clinical trials. In the CLOSE-1 study protocol, eye pain experienced by the subjects at Day 8 compared to placebo is defined as the study's key secondary objective.

Pain is considered a personal and highly subjective experience. The essential requisite for valid interpretation and analysis of VAS ratings obtained throughout the study is to ensure reliable and valid assessments of eye pain.

Different studies (Jensen et al., 2003, Aicher et al., 2011) have been performed to establish preliminary consensus on the cut-offs at which VAS pain scores could be considered no pain, mild, moderate, and severe pain.

Aicher and colleagues categorized VAS pain scores as follows: no pain 0-2 mm, mild pain 2-17 mm, moderate pain 17-47 mm, severe pain 47-77 mm, very severe pain 77-96 mm, and most severe imaginable pain 96-100 mm. On the other hand, Jensen and colleagues concluded that any VAS pain score of 0-4 mm tended to be labeled as no pain.

Based on the previous scientific investigations, the below additional secondary objectives shall be analyzed to complete the evaluation of the eye pain assessment currently described in both, the CLOSE- 1 study protocol and the Statistical Analysis Plan.

These additional analyses shall also help to check the consistency of eye pain assessment by means of a continuous variable (0-100 mm VAS) and its analysis from a dichotomic perspective (no pain VAS=0/pain VAS>0) and from the perspective of the continuous variable the eye pain VAS score is.

- (Proportion of patients with VAS pain score of "0-0.2 cm" (no eye pain) compared to placebo at Day 3, Day 8, Day 15 and Day 29)

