Between treatment comparison of the evolution over time will be analysed using a Restricted Maximum Likelihood (REML)-based repeated measures approach (Mixed Model Repeated Measures [MMRM]). The model for analysis will include the change from baseline as a dependent variable, the baseline score as a cavariate, the categorical fixed effects of treatment (IMP, Placebo) and visit and the interaction treatment*visit. An unstructured (co)variance structure will be used to model the within-patient errors. If this analysis fails to converge, alternative covariance structures will be tested. Akaike's information criterion will be used to determine the best fit (smaller AIC).

If it is not possible to apply a MMRM due to the non-normality of the variable, the Mann Whitney Wilcoxon test will be performed.

Secondary efficacy analyses will be performed on the FAS population.

The PP population set will be also tested to confirm the robustness of the secondary analyses.

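### The SAP assigns secondary efficacy to two different populations, and the table list follows the one that deletes rescued patients, including for the sensitivity analysis

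*SAP*

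**What the plan says.** SAP section 5 defines a reduced set: "The FAS non-RM will be the analysis set for the efficacy endpoints and will include all randomized patients without including rescued subjects". The definition ends in an unclosed bracket and states no time limit. By contrast, the Visit 3 per-protocol set in the same section is limited by time: "without the use of rescue/prohibited medication until visit 3".

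On the population for secondary efficacy, the SAP says two things:

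- Section 5: "Secondary efficacy analysis will be performed analyzing all subjects included in the FAS non-RM populations".
- Section 6.3.6.2: "Secondary efficacy analyses will be performed on the FAS population". Protocol 9.1.12 says the same.

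Section 5 also names the FAS as the primary efficacy population and puts the sensitivity analysis on the FAS. Section 6.3.7 lists use of rescue and prohibited medication among the events that the sensitivity analysis covers. In section 8.1, however, Table 14.2.18, the Day 8 cell-grade sensitivity analysis, has FAS non-RM in its population column.

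Protocol 6.7.2 gives the status of rescue: "Rescued patients will be considered treatment failures, but the need for rescue therapy will not be considered an AE". It also asks investigators to make sure that "the patient will attend all his/her remaining study visits until study completion, aiming to collect the most complete efficacy and safety data". The Missing data paragraph of the protocol synopsis says that "the primary measure is a responder measure where rescue is considered treatment failure".

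**The concern.** A programmer cannot follow both section 5 and section 6.3.6.2. SAP 6.1 says "The SAP presented in this document will supersede the statistical analysis methods described in the clinical protocol", which ranks the SAP above the protocol but does not rank two sections of the SAP against each other.

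The choice matters because rescue is given to patients who do not respond adequately. Removing them after randomisation selects each arm on its own outcome, so the comparison is no longer between randomised groups. It also discards the post-rescue data that sites are asked to collect. With no time limit in the definition, a patient rescued after Day 15 would drop out of the Day 3 and Day 8 tables as well.

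For most inflammation-sign, photophobia and visual-acuity results, FAS non-RM is the only population listed. The only legible sensitivity table cannot show the effect of rescue, because its set contains no rescued patient.

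**Working it through.** **Count of tables (SAP 8.1).** Rows listed on FAS non-RM only:

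| Tables | Number |
|---|---|
| 14.2.4.x | 2 |
| 14.2.5.x | 2 |
| 14.2.6 to 14.2.8 | 3 |
| 14.2.9.x | 5 |
| 14.2.10.x | 5 |
| 14.2.11.x | 10 |
| 14.2.12, 14.2.13 | 2 |
| 14.2.14 | 1 |
| **Total** | **30** |

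Seven of these (14.2.4.2, 14.2.5.2, 14.2.11.2, .4, .6, .8 and .10) are descriptive, with no test. Table 14.2.14 is counted as listed, although SAP 6.1 plans its by-visit VAS comparison for both sets; without it the count is 29. Rows 14.2.15.1 to 14.2.17 are broken in the available text and are not counted. FAS versions are legible for 14.2.3.2, 14.2.3.4, 14.2.19.2 and 14.2.20.2.

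**Effect of deletion on a responder rate.** The documents give no rescue rates, and no response rates for the affected endpoints, so these are assumed. Randomised numbers are 140 and 70 (protocol 9.1.1). Let p be the FAS responder rate in an arm and r its rescue rate, and let every rescued patient be a non-responder at the visit. The responders stay and the denominator shrinks, so

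FAS non-RM rate = p / (1 − r).

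Example at 5%/30% rescue (active/placebo): 0.60/0.95 − 0.40/0.70 = 63.2% − 57.1% = 6.0 points, against 20 on the FAS.

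| FAS rates (difference) | 5%/30% | 10%/20% | 20%/20% |
|---|---|---|---|
| 50% vs 30% (20) | 9.8 | 18.1 | 25.0 |
| 60% vs 40% (20) | 6.0 | 16.7 | 25.0 |
| 70% vs 50% (20) | 2.3 | 15.3 | 25.0 |
| 22% vs 7% (15) | 13.2 | 15.7 | 18.75 |

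The last row uses the plan's own sample-size rates for the primary endpoint. It is for scale only, because that endpoint's FAS test is not in question.

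**Behaviour under a null.** Suppose the FAS rate, with rescue counted as failure, is 22% in both arms. I enumerated both binomials and applied the uncorrected Pearson chi-square test at two-sided 0.05:

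| Rescue, active/placebo | n | Rejects | Favours active | Favours placebo |
|---|---|---|---|---|
| FAS, none deleted | 140/70 | 5.1% | 2.3% | 2.8% |
| 10%/10% | 126/63 | 5.0% | 2.4% | 2.6% |
| 5%/20% | 133/56 | 10.8% | 0.5% | 10.3% |
| 20%/5% | 112/66 | 9.2% | 8.7% | 0.5% |

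This is a null for the composite only. Where rescue rates differ, the non-rescued patients do differ in response rate, and the test detects that.

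**Cases that go the other way.** If all rescue comes after the visit, in patients who respond like the others, the difference at that visit does not change. If observed values after rescue are used, deletion can lower a rate. With 30% rescued, 80% of them and 50% of the others clear at Day 29, the FAS rate is 0.7 × 0.50 + 0.3 × 0.80 = 59%, against 50% on FAS non-RM.

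**The case against.** The strongest objection concerns the comparator. The condition that a responder must not have received rescue is written into the primary and key secondary analyses only (SAP 6.3.5 and 6.3.6.1). The synopsis ties rescue-as-failure to the primary measure, SAP 6.3.6.2 defines improvement by change in grade alone, and SAP 6.6 plans no imputation. A FAS version of Table 14.2.4.1, run as written, might therefore use observed values after rescue, and the point differences above would not follow. This stands as a limit on the illustration. It also shows a second gap: the rescue rule for these endpoints has to be stated whichever set is used. Protocol 6.7.2 is general in calling rescued patients treatment failures.

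The endpoints are exploratory and no multiplicity control is planned, so no confirmatory error rate is at stake. That is correct and limits the weight of the point. It does not make two conflicting populations workable.

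Tables 14.2.1.1 (FAS) and 14.2.1.3 (FAS non-RM), read side by side, already show what deletion does to the Day 8 primary result. That is true, but it is a comparison of two sets. It does not repair a sensitivity table whose listed population contradicts section 5.

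Finally, naming one population would by itself remove the contradiction, and the rescue strategies proposed below are design choices. That is fair: other choices are possible, but one has to be written down.

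**Conclusion.** The point holds and should be fixed. The contradiction inside the SAP, the 30 tables listed on FAS non-RM only, and the population of Table 14.2.18 all follow from the text and rest on no assumption. The size of the effect does rest on assumed rescue and response rates. Under them, a 20-point FAS difference appears as anything from 2.3 to 25.0 points, and the direction depends on each arm's rescue rate, its timing and the values of rescued patients. The bias therefore cannot be signed in advance.

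The consequence is limited to exploratory endpoints and the sensitivity analysis. The primary and key secondary tests keep their FAS tables (14.2.1.1 and 14.2.2.1), and sections 6.3.5 and 6.3.6.1 give the FAS non-RM versions no role.

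**What to change.** 1. In SAP section 5, name the FAS as the population for secondary efficacy, in line with 6.3.6.2 and protocol 9.1.12. List Tables 14.2.4.1 to 14.2.14 on the FAS and keep FAS non-RM versions only as supplementary.
2. For responder endpoints (cell grade 0, cell and flare thresholds, VAS pain 0, no discomfort, improvement yes/no), count rescue before the visit as non-response. For sign-frequency and grade tables, use observed data on the FAS and do not assign signs or grades that nobody observed.
3. For the MMRM endpoints, state one rescue strategy that keeps pre-rescue data: for example, all observed values, or only post-rescue values set to missing.
4. Put Table 14.2.18 on the FAS with a named rescue strategy that differs from the primary analysis, such as the observed outcome regardless of rescue. Otherwise it would repeat 14.2.1.1.
5. State in one line that 14.2.1.3 and 14.2.2.3 are supplementary to the FAS tables.

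The PP definition can stay as it is. SAP 6.3.6.2 and protocol 9.1.12 also promise PP analyses of the secondary endpoints, and no legible secondary table lists that set, so this can be settled in the same edit.

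Cost: SAP wording, population labels on 30 table shells plus 14.2.18, and some programming for the rescue-date rule, the MMRM strategy and any supplementary copies. There is no new data collection and no change to sample size or alpha. Results may move in either direction.
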